CLINICAL PROTOCOL M16-300

Protocol Number	M16-300
Version and Date	Version 3, 01-DEC-2017
Protocol Title	A Phase 1/2 Study on the Safety of Rovalpituzumab Tesirine Administered in Combination with Nivolumab or Nivolumab and Ipilimumab for Adults with Extensive-Stage Small Cell Lung Cancer
Investigational Drugs	Rovalpituzumab tesirine (SC16LD6.5) Nivolumab (BMS-936558, MDX1106, ONO-4538, Opdivo®) Ipilimumab (MDX-010, Yervoy®)
Phase	1/2
EUDRA CT Number	2016-003686-26
CRO Medical Monitors	
Sponsor	AbbVie* [name]
Sponsor Representative	

This study will be conducted in compliance with the protocol, Good Clinical Practice and all other applicable regulatory requirements, including the archiving of essential documents.

*The specific contact details of the AbbVie legal/regulatory entity (person) within the relevant country are provided within the clinical trial agreement with the Investigator/Institution and in the Clinical Trial Application with the Competent Authority. "AbbVie" shall mean AbbVie Inc. or its affiliate AbbVie Stemcentrx LLC.

Confidential Information

No use or disclosure outside AbbVie is permitted without prior written authorization from AbbVie.

Synopsis

TITLE: A Phase 1/2 Study on the Safety of Rovalpituzumab Tesirine Administered in Combination with Nivolumab or Nivolumab and Ipilimumab for Adults with Extensive-Stage Small Cell Lung Cancer				
PROTOCOL NUMBER: M16-300				
PHASE OF DEVELOPMENT: 1/2				
INVESTIGATORS AND STUDY CENTERS: Multicenter				
OBJECTIVES:				
Primary:				

 • To assess the safety of rovalpituzumab tesirine when administered in combination with nivolumab or nivolumab and ipilimumab in adult subjects with extensive-stage small cell lung cancer (SCLC) 				
Secondary:				

 • To explore the efficacy of rovalpituzumab tesirine when administered in combination with nivolumab or nivolumab and ipilimumab in adult subjects with extensive-stage SCLC 				
Exploratory:				

 • To explore the expression of DLL3 and PD-L1 in SCLC and their relationship to clinical outcome during treatment • To explore the pharmacokinetics (PK) of and incidence of anti-therapeutic antibodies (ATA) against rovalpituzumab tesirine, nivolumab, and ipilimumab • To explore the effect of study drug regimen on disease and immune biomarkers 				
TEST PRODUCTS, DOSE, AND MODE OF ADMINISTRATION:				

 • Rovalpituzumab tesirine 0.3 mg/kg will be administered intravenously (IV) on Day 1 of the first and third 3-week cycle (q6wk x 2), or per other dosing regimen recommended by the safety monitoring committee (SMC) • Nivolumab 1 mg/kg or 360 mg IV q3wk or 480 mg IV q4wk as monotherapy • Ipilimumab 1 mg/kg or 3 mg/kg IV q3wk x 4 cycles • Dexamethasone 8 mg orally (PO) twice daily (BID) on Day -1, Day 1 (the day of dosing), and Day 2 of each cycle in which rovalpituzumab tesirine is administered. 				
STUDY DESIGN AND METHODOLOGY:				
This is a multicenter study involving rovalpituzumab tesirine administered in combination with nivolumab or nivolumab and ipilimumab in subjects with SCLC. Planned cohorts are indicated below.				
Cohort	Population	Rovalpituzumab tesirine	Nivolumab	Ipilimumab
1	2 nd line or later SCLC (Platinum-failure)	0.3 mg/kg q6wk x 2	360 mg q3wk beginning on Week 4 (Cycle 2) x 2 cycles, then 480 mg q4wk	—
2	2 nd line or later SCLC (Platinum-failure)	0.3 mg/kg q6wk x 2	1 mg/kg q3wk x 4 cycles beginning on Week 4 (Cycle 2), then 480 mg q4wk (monotherapy) after 6 week washout	1 mg/kg q3wk x 4 beginning on Week 4 (Cycle 2)
3	2 nd line or later SCLC (Platinum-failure)	0.3 mg/kg q6wk x 2	1 mg/kg q3wk x 4 cycles beginning on Week 4 (Cycle 2), then 480 mg q4wk (monotherapy) after 8 week washout	3 mg/kg q3wk x 4 beginning on Week 4 (Cycle 2)

Initially, up to 12 subjects will be enrolled into Cohort 1 in order to obtain 6 evaluable subjects through the DLT evaluation period of 12 weeks, after which an SMC will perform a safety review of the data. The SMC may recommend further evaluation of the safety of a given combination or dose regimen, investigation of alternative dose regimens, a modification of the dosing interval, or a change in the maximum number of doses (or elimination) of any component of the regimen. Based on the tolerability of the initial 6 evaluable subjects in Cohort 1, enrollment may begin of up to 12 subjects into Cohort 2 to obtain 6 evaluable subjects through the DLT evaluation period of 12 weeks. Once Cohort 2 opens, Cohort 1 may continue enrolling (up to 30 subjects total). Similarly, Cohort 3 may enroll up to 12 subjects upon review of the tolerability of the first 6 evaluable subjects in Cohort 2. Once Cohort 3 is open, Cohort 2 may continue enrolling (up to 30 subjects total). Following completion of the DLT evaluation period and SMC review for a given cohort, the SMC may recommend that enrollment into the expansion of the cohort be initiated to gather additional safety data prior to escalation to the next cohort. Based on the tolerability of the initial 6 evaluable subjects in Cohort 3, Cohort 3 may continue enrolling (up to 30 subjects total). If $\leq 1/6$ subjects being evaluated in each cohort experience a DLT within the first 4 cycles of treatment (12 weeks), enrollment beyond 12 subjects may proceed. The SMC will meet at a frequency outlined in the SMC Charter and will periodically monitor the safety and tolerability of the dose regimen to endorse continued enrollment in the cohorts. In general, if a regimen appears intolerable, the dose of rovalpituzumab tesirine may be reduced to dose level -1, 0.2 mg/kg. Such changes will constitute a new cohort, and subsequent cohorts may then carry forward the tolerated dose. For instance, if Cohort 1 is not tolerated, a new Cohort 4 consisting of rovalpituzumab tesirine 0.2 mg/kg and nivolumab 360 mg q3wk could be initiated; if tolerated, a new Cohort 5 consisting of rovalpituzumab tesirine 0.2 mg/kg, nivolumab 1 mg/kg and ipilimumab 1 mg/kg q3wk (nivolumab and ipilimumab doses from Cohort 2) could then be initiated.

For each cohort and dose regimen, up to 30 total subjects may be enrolled as part of an expansion phase after evaluation of the tolerability of the first 6 evaluable subjects. Details regarding enrollment priorities are discussed in Section 3.1.

MAJOR ELIGIBILITY CRITERIA:

Subjects with histologically or cytologically confirmed, 2nd line or later extensive-stage SCLC with evaluable or measurable disease; Eastern Cooperative Oncology Group (ECOG) 0-1; adequate hematologic, hepatic, and renal function; no active, known, or suspected autoimmune disease; and no prior exposure to an immuno-oncology or pyrrolbenzodiazepine (PBD)-based drug.

PLANNED SAMPLE SIZE:

Up to approximately 90 subjects (up to approximately 30 subjects per cohort)

STUDY TESTS AND OBSERVATIONS:

Safety assessments (Section 2.4.1) include physical exam, vital signs, body weight, ECOG performance status, clinical adverse events (AEs), laboratory tests, electrocardiograms (ECGs), echocardiogram, Fluid Retention Questionnaire, and monitoring of concomitant medications.

Efficacy assessments will consist of radiographic imaging. Responses will be categorized by Response Evaluation Criteria in Solid Tumors (RECIST) v1.1 (Eisenhauer, 2009). See Section 6.4.6 for imaging schedule per cohort.

Blood samples for PK, immunogenicity, biomarker, and pharmacodynamics (PD) assessments will be collected at protocol-defined time points to support the study endpoints. Sensitive, validated assays will be used to measure blood concentrations of rovalpituzumab tesirine antibody-drug conjugate (ADC) and related analytes of rovalpituzumab tesirine, such as total antibody and SC-DR002, as applicable. A validated immunoassay will be used to assess ATA against rovalpituzumab tesirine. Analogous assays may be performed for nivolumab and/or ipilimumab.

Pharmacodynamic and biomarker assessments will include analyses of tumor tissue for DLL3 and PD-L1 expression, and of blood samples for tumor markers, circulating tumor cells (CTC), immune, and soluble biomarkers such as soluble DLL3.

STATISTICAL METHODS:

As a general strategy, data will be analyzed by cohort and dose regimen.

Safety analysis will include summaries by cohort and dose regimen of: AEs, laboratory measures, physical examinations, ECG, and vital signs using data from subjects in the Safety Analysis set. The incidence of DLTs will be summarized.

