3.1 Summary of Study Design

This is a multicenter study involving rovalpituzumab tesirine administered in combination with nivolumab or nivolumab and ipilimumab in subjects with SCLC. The study plans to include 3 cohorts of up to approximately 30 subjects each (Table 1). DLTs will be assessed during the DLT Evaluation Period (Section 3.1.1).

Figure 1. Study Schema

- * Up to 12 DLL3+ subjects will be enrolled into each cohort in order to obtain 6 evaluable subjects at the end of the 12 week DLT period.
- a. Based on the tolerability of the initial 6 DLL3+ subjects in cohort 1, enrollment may begin of up to 12 DLL3+ subjects into cohort 2. The same strategy will be used for cohort 3 enrollment. If a regimen appears intolerable, the dose of rovalpituzumab tesirine may be reduced to 0.2 mg/kg, or 0.1 mg/kg. Such changes will constitute a new cohort, and subsequent cohorts may then carry forward the tolerated dose.
- b. For each cohort, up to 30 total subjects may be enrolled as part of an expansion phase after evaluation of the tolerability of the first 6 evaluable subjects.

Table 1. Planned Cohorts in the Study

Cohort	Population	Rovalpituzumab tesirine	Nivolumab	Ipilimumab
1	2 nd line or later SCLC (Platinum-failure) (Section 4.1)	0.3 mg/kg q6wk x 2	360 mg q3wk beginning on Week 4 (Cycle 2) x 2 cycles, then 480 mg q4wk	–
2	2 nd line or later SCLC (Platinum-failure) (Section 4.1)	0.3 mg/kg q6wk x 2	1 mg/kg q3wk x 4 cycles beginning on Week 4 (Cycle 2), then 480 mg q4wk (monotherapy) after 6 week washout	1 mg/kg q3wk x 4 beginning on Week 4 (Cycle 2)
3	2 nd line or later SCLC (Platinum-failure) (Section 4.1)	0.3 mg/kg q6wk x 2	1 mg/kg q3wk x 4 cycles beginning on Week 4 (Cycle 2), then 480 mg q4wk (monotherapy) after 8 week washout	3 mg/kg q3wk x 4 beginning on Week 4 (Cycle 2)

Initially, up to 12 subjects will be enrolled into Cohort 1 in order to obtain 6 evaluable subjects through the DLT evaluation period of 12 weeks. If $\leq 1/6$ subjects being evaluated has a DLT, enrollment beyond 12 subjects may proceed (i.e., enrollment into Cohort 1 expansion may begin). Subjects who are considered DLT-inevaluable (e.g., due to withdrawal from study before completing the DLT evaluation period; see Section 3.1.1) will be replaced if required.

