3.1.1 Definition of Dose-Limiting Toxicities

The DLT evaluation period is the first 12 weeks of treatment for all subjects. DLTs are defined as any of the following in the DLT-evaluation period, graded according to the National Cancer Institute's Common Terminology Criteria for Adverse Events (NCI CTCAE), version 4.03 (see Appendix 13.6)

- Grade 4 thrombocytopenia (or Grade 3 thrombocytopenia with bleeding) lasting more than 7 days and/or requiring platelet transfusion
- Grade 4 neutropenia lasting more than 7 days, and/or requiring hematopoietic growth factor rescue, or any febrile neutropenia (Grade 3 or 4 neutropenia with concurrent fever $\geq 38.3^{\circ}\text{C}$)
- Grade 4 anemia unrelated to underlying disease

- Clinically-significant Grade 3 or 4 non-hematologic laboratory abnormality that does not resolve to Grade 0/1 or baseline within 7 days
- Grade 3 or 4 non-laboratory AE with the exception of fatigue, asthenia, nausea, or other manageable constitutional symptom

The following events will not be considered DLTs:

- Any AE \geq Grade 3 clearly determined to be unrelated to study drug(s) (e.g., disease progression)
- \geq Grade 3 isolated alkaline phosphatase, amylase, or lipase laboratory abnormality of any duration
- \geq Grade 3 endocrinopathies controlled by hormone replacement
- Grade 3-4 electrolyte abnormalities

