5.1.1 Treatment Regimen Descriptions for Each Cohort

The schedule, dose, route, and cycle length for the treatment regimens in each of the three cohorts are summarized below in [Table 2](#).

Table 2. Study Drug Dosing Schedule

Cohort	Study Drug(s)	Cycle					
		1	2	3	4	5	6+
1 ^a	Rovalpituzumab tesirine 0.3 mg/kg	X		X			
	Nivolumab 360 mg q3wk		X	X			
	Nivolumab 480 mg q4wk				X	X	X
2 ^b	Rovalpituzumab tesirine 0.3 mg/kg	X		X			
	Nivolumab 1 mg/kg		X	X	X	X	
	Ipilimumab 1 mg/kg		X	X	X	X	
	Nivolumab 480 mg q4wk ^d						X
3 ^c	Rovalpituzumab tesirine 0.3 mg/kg	X		X			
	Nivolumab 1 mg/kg		X	X	X	X	
	Ipilimumab 3 mg/kg		X	X	X	X	
	Nivolumab 480 mg q4wk ^e						X

- a) Cycles 1–3 are 3 weeks. Cycles 4 and beyond are 4 weeks.
- b) Cycles 1–5 are 3 weeks. Cycles 6 and beyond are 4 weeks
- c) Cycles 1–5 are 3 weeks. Cycles 6 and beyond are 4 weeks
- d) Nivolumab 480 mg q4wk (monotherapy) to be started 6 weeks after Cycle 5 Day 1 in Cohort 2.
- e) Nivolumab 480 mg q4wk (monotherapy) to be started 8 weeks after Cycle 5 Day 1 in Cohort 3.

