6.4.6 Efficacy Assessment and Tumor Response

On applicable cycles, disease assessment will occur at least 3 days, but no greater than 7 days, prior to day of dosing.

Cohort 1 Imaging Schedule:

- Prior to Cycle 3 Day 1 (6 weeks after Screening imaging)
- Prior to Cycle 5 Day 1 (7 weeks after Cycle 3 Day 1 imaging)
 - If response is noted (CR or PR) on Cycle 5 Day 1 scan, a mandatory 4 week follow up scan will be performed to confirm response. The 4 week follow up scan may be omitted if no response is noted on Cycle 5 Day 1 scan.
- Prior to Cycle 7 Day 1 (8 weeks after Cycle 5 Day 1 imaging)
- After Cycle 5 Day 1, imaging will be collected every 8 weeks (at least 3 days, but no greater than 7 days, prior to day of dosing) during the maintenance therapy stage of the study.

Cohort 2 Imaging Schedule:

- Prior to Cycle 3 Day 1 (6 weeks after Screening imaging)
- Prior to Cycle 5 Day 1 (6 weeks after Cycle 3 Day 1 imaging)

- Prior to Cycle 6 Day 1 (6 weeks after Cycle 5 Day 1 imaging given washout period)
- Prior to Cycle 8 Day 1 (8 weeks after Cycle 6 Day 1 Imaging)
- After Cycle 8 Day 1, imaging will be collected every 8 weeks (at least 3 days, but no greater than 7 days, prior to day of dosing) during the maintenance therapy stage of the study.

Cohort 3 Imaging Schedule:

- Prior to Cycle 3 Day 1 (6 weeks after Screening imaging)
- Prior to Cycle 5 Day 1 (6 weeks after Cycle 3 Day 1 imaging)
 - If response is noted (CR or PR) on Cycle 5 Day 1 scan, a mandatory 4 week follow up scan will be performed to confirm response. The 4 week follow up scan may be omitted if no response is noted on Cycle 5 Day 1 scan.
- Prior to Cycle 6 Day 1 (8 weeks after Cycle 5 Day 1 imaging given washout period)
- Prior to Cycle 8 Day 1 (8 weeks after Cycle 6 Day 1 imaging)
- After Cycle 8 Day 1, imaging will be collected every 8 weeks (at least 3 days, but no greater than 7 days, prior to day of dosing) during the maintenance therapy stage of the study.

Disease assessment will consist of the following:

- CT scans of the chest, abdomen, and pelvis (and neck if indicated) (Section 7.2)
- MRI of the brain – if clinically indicated (e.g. if CNS progression has been documented previously). CT of the brain with IV contrast may be substituted at the discretion of the study doctor.

Tumor response will be determined and categorized by RECIST v1.1 (Eisenhauer, 2009).

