			Day -14 to -1	Day -1		Day 1 (±2 d)	Day 2 ¹	Day 8 ³ (±2 d)	Day 15 ³ (±2 d)			
	Circulating Tumor Cells ⁴⁴					X ⁴⁵					X	
	Genotyping ⁴⁶		X									
	Serosal Fluid ⁴⁷					X		X		X		
	Cell Free Circulating Tumor DNA (ctDNA) ⁴⁸					X					X	

Table Notes

* **Cycles 1 – 3 are 3 weeks. Cycles 4 and beyond are 4 weeks.**

- 1) Only applies to Cycle 1 and Cycle 3 when rovalpituzumab tesirine is administered.
- 2) EOT occurs within 7 days of documentation of the decision to discontinue treatment.
- 3) Visits on Days 8 and 15 should be done during Cycles 1 and 3 only (may be omitted during cycles that do not include rovalpituzumab tesirine).
- 4) LTFU includes the 100 day follow up for safety; LTFU also occurs q6wk (±1 week) until 6 months, then q12wk (±1 week) until disease progression, initiation of new anticancer therapy, or withdrawal/termination from the study. Disease/Response Assessment consists of subsequent anticancer therapies and dates, date of progression (if not already captured on study), and survival status. Subjects will be followed for survival until death or study termination, whichever occurs first. After disease progression, subjects who are not retreated will be followed (Section 6.6).
- 5) This may be a telephone follow-up or performed in clinic.
- 6) Prescreening ICF only.
- 7) Informed consent for the main portion of this study will be obtained prior to the performance of any study procedures and may occur within 30 days prior to the Day 1 Visit. All other screening procedures must occur within 14 days prior to Day 1.
- 8) Confirmation of study eligibility per inclusion/exclusion criteria.
- 9) Medical and Surgical History includes descriptions of conditions or procedures, and dates of onset - offset.
- 10) Malignancy History includes tumor type, stage, sites of metastases, mutational status.
- 11) Prior Anticancer Treatments include names of specific treatments, dates of administration, response to therapy, and DOR, if known.

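### The Synopsis expansion rule equates the first four cycles with 12 weeks, but in Cohort 1 four cycles last 13 weeks

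*Combined protocol and SAP*

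**What the plan says.** The Synopsis (Study Design and Methodology) gives the numerical rule for going past the first 12 subjects. It applies to each cohort and allows expansion if at most 1 of the 6 subjects under evaluation "experience a DLT within the first 4 cycles of treatment (12 weeks), enrollment beyond 12 subjects may proceed".

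Section 3.1.1 defines the window in weeks only: "The DLT evaluation period is the first 12 weeks of treatment for all subjects". It then ties the term DLT to that window: "DLTs are defined as any of the following in the DLT-evaluation period". Section 3.1 states the rule for Cohort 1 without mentioning cycles and enrols up to 12 subjects "in order to obtain 6 evaluable subjects through the DLT evaluation period of 12 weeks".

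Cycle length differs by cohort. Table 2 in Section 5.1.1 has, for Cohort 1, "Cycles 1–3 are 3 weeks. Cycles 4 and beyond are 4 weeks" (note a) and, for Cohorts 2 and 3, "Cycles 1–5 are 3 weeks. Cycles 6 and beyond are 4 weeks" (notes b and c). The Cohort 1 Schedule of Assessments (Section 13.1.1) repeats note a. The Cohort 1 imaging schedule in Section 6.4.6 fits the same calendar: "Prior to Cycle 5 Day 1 (7 weeks after Cycle 3 Day 1 imaging").

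**The concern.** The Synopsis sentence measures one window in two units and treats them as equal in every cohort. If they differ in any cohort, a toxicity in the gap is inside the window by cycles and outside it by weeks. The rule tolerates only one subject with a DLT among six, so one event in the gap could move the count from 1 of 6 to 2 of 6. Safety is the primary objective, and Cohort 1 is the first cohort reviewed. Its six evaluable subjects inform both the expansion of Cohort 1 and the decision to open Cohort 2, so the boundary of the window should not be open to two readings.

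**Working it through.** **Inputs.** Planned cycle lengths come from Table 2 (Section 5.1.1) and Section 13.1.1, the imaging intervals from Section 6.4.6, the 12-week window from Sections 3.1 and 3.1.1, and the limit of 1 in 6 from the Synopsis and Section 3.1.

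**Step 1: length of the first four cycles.**
- Cohorts 2 and 3: 3 + 3 + 3 + 3 = 12 weeks, Days 1–84. The Synopsis figure reproduces.
- Cohort 1: 3 + 3 + 3 + 4 = 13 weeks, Days 1–91. It does not reproduce.
- Cross-check for Cohort 1: 6 weeks from screening imaging to the Cycle 3 scan plus 7 weeks to the Cycle 5 scan = 13 weeks. Planned Cycle 5 Day 1 is Day 92.

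The two units differ by one week, Days 85–91, in Cohort 1 only.

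**Step 2: how often that week would decide the result.** The documents give no DLT rate, so the 12-week risk R is an assumption. With a constant hazard, the weekly risk is w = 1 − (1 − R)^(1/12) and the 13-week risk is R13 = 1 − (1 − R)^(13/12).

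The main route to a changed result is exactly one of six subjects with a DLT by Week 12 and at least one of the other five with a first event in Week 13:

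6R(1 − R)^5 × [1 − (1 − w)^5]

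| Assumed R | Exactly 1 of 6 by Week 12 | At least 1 of the other 5 in Week 13 | Product |
|---|---|---|---|
| 0.05 | 0.232 | 0.021 | 0.005 |
| 0.10 | 0.354 | 0.043 | 0.015 |
| 0.20 | 0.393 | 0.089 | 0.035 |
| 0.25 | 0.356 | 0.113 | 0.040 |
| 0.33 | 0.267 | 0.154 | 0.041 |

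**Step 3: check through the pass probability.** P(pass) = (1 − p)^6 + 6p(1 − p)^5, with p = R and then p = R13:

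| Assumed R | R13 | Pass, 12 weeks | Pass, 13 weeks | Difference |
|---|---|---|---|---|
| 0.05 | 0.054 | 0.967 | 0.962 | 0.005 |
| 0.10 | 0.108 | 0.886 | 0.870 | 0.016 |
| 0.20 | 0.215 | 0.655 | 0.619 | 0.036 |
| 0.25 | 0.268 | 0.534 | 0.492 | 0.042 |
| 0.33 | 0.352 | 0.358 | 0.315 | 0.042 |
| 0.40 | 0.425 | 0.233 | 0.196 | 0.037 |

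The differences slightly exceed the products in Step 2 because they also include the case of no DLT by Week 12 and two or more in Week 13. Both calculations give about 0.5% at R = 0.05 and about 4% at R = 0.20 to 0.33, which is close to the maximum.

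**The case against.** The strongest reply is that Section 3.1.1 already settles the matter. DLT is a defined term, limited to events in the first 12 weeks. On that definition a Week 13 toxicity is not a DLT at all, so it cannot be one within the first four cycles. The Synopsis parenthesis itself says 12 weeks, and so do the other mentions of the window in the Synopsis, Figure 1 and Section 3.1. This largely stands. It makes 12 weeks the likely intent and the cycle wording a lone outlier. It does not make the Synopsis equality true for Cohort 1, and the sentence still offers a second boundary inside a numerical decision rule.

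A reader might infer more than the documents support:

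- **That one Week 13 event would block the triplet cohorts.** The 1-of-6 count governs enrolment beyond 12 subjects. Cohort 2 opens on the tolerability of the initial six evaluable subjects in Cohort 1, and no count is written into that step.
- **That a Week 13 event would escape review.** Section 3.1 has the safety monitoring committee look at cumulative safety data beyond the DLT window.
- **That the committee would pick whichever reading suited it.** The trial is open-label, but nothing in the documents shows or predicts this.
- **That dose delays widen the gap.** Section 5.5.1 restarts nivolumab and ipilimumab at the next regularly scheduled visit and does not replace skipped doses. Section 5.5.3 does not require their delay when rovalpituzumab tesirine is delayed at Cycle 3. No passage says that delays shift the cycle calendar.

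**Conclusion.** The Synopsis figure is wrong as written for Cohort 1: four planned cycles are 13 weeks, and the disputed period is Days 85–91. That part is plain arithmetic on planned cycle lengths and is confirmed in three places. Cohorts 2 and 3 are unaffected.

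The consequence is modest. On the assumed rates, Week 13 would decide the 1-of-6 result in about 0.5% to 4% of cases, and only if the cycle wording were applied in place of the Section 3.1.1 definition. These figures rest on a constant hazard, independent subjects and six subjects followed through both windows. An uneven hazard would change them in a direction that the documents do not allow one to state. The direct effect is on Cohort 1 expansion; any effect on opening Cohort 2 runs through a tolerability judgement in the same six subjects. The point deserves correction because the slip sits in a decision rule of a trial with safety as its primary objective, not because a wrong decision is likely.

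**What to change.** Before the Cohort 1 review, reconcile the Synopsis sentence with Section 3.1.1 so that both give the same DLT window in one unit, and remove the equation of four cycles with 12 weeks for Cohort 1. Which window applies is for the sponsor to decide; this point does not favour a longer or shorter one. If the 12-week window is kept, the cost is one phrase in the Synopsis, since Sections 3.1 and 3.1.1 already agree. If a cycle-based window is chosen instead, those sections and the other 12-week statements would have to follow, with the 13-week length stated for Cohort 1.
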